- Cardiac CT with contrast and cardiac MRI. These imaging studies will be performed through NHLBI protocols 12-H-0141 (“Prospective Evaluation of New Techniques in Radiation Reduction for Cardiovascular Computed Tomographic Angiography”) for cardiac CT and 02-H-0050 (“Technical Development of Cardiovascular Magnetic Resonance Imaging”) for cardiac MRI.
- Echocardiogram and electrocardiogram will be performed on every visit except the one week follow up.

These outcome measures will be assessed using RECIST criteria at every scheduled admission except the 1 week visit.

In addition, the following studies will be performed on all patients, but will serve as exploratory outcome measures, since RECIST criteria are not adequate:

Performed at baseline, 1, 2, 4, 6, 8, 10 and 12 months:

- Pulmonary function tests, echocardiogram, and electrocardiogram to evaluate cardiopulmonary function

Performed at baseline, 2, 4, 6, 8, 10 and 12 months:

- Whole body technetium 99-MDP bone scan to assess bone involvement.
- Whole body 18-FDG PET scan including brain to evaluate for visceral involvement.

Studies performed at 15, 18 and 24 months (off therapy) follow up visits will include:

- Chest, cardiac, abdomen or pelvic CT with contrast depending on the location of the target lesion followed on each case.
- Brain, cerebellar, pituitary or orbital MRI with gadolinium depending on the location of the target lesion followed on each case.
- Whole body technetium 99-MDP bone scan to assess bone involvement and whole body 18-FDG PET scan including brain to evaluate for visceral involvement. These 2 modalities will help in determining disease recurrence according to the degree of uptake of the T-99MDP and FDG.
- Pulmonary function tests, 6 minute walk, echocardiogram, and electrocardiogram to evaluate cardiopulmonary function

Consultations for all patients in this treatment trial will include an ophthalmology examination to evaluate orbital and optic nerve involvement as well as possible side effects of the trial therapy. All patients will be evaluated by neurology and dermatology, to assess the extent of disease and to evaluate response and side effects during therapy. All patients will also see the Rehabilitation Medicine service for a 2-hour assessment, with evaluations by physical therapy, occupational therapy and, if indicated, speech and language pathology.

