Progression-free Survival at 12 mo. % (95% CI)	9 (3-20)	26 (15-39)	41 (27-54)
CR or PR Patients (% [95% CI])	29 (54 [40-67])	27 (50 [36-64])	41 (76 [62-86])
Duration of response Median months (95% CI)	5.6 (4.5-7.4)	9.5 (7.4-NA)	10.5 (7.4-14.9)

5.6.1.3- Trametinib Dimethyl Sulfoxide (GSK1120212B, MEKINIST)²⁵

The RAF-MEK-ERK pathway plays a critical role in multiple cellular functions. Activation of the pathway can result from activating mutations of the upstream receptor tyrosine kinases (RTKs) and RAS, or upregulation/mutations in RAF and MEK. Upon activation, RAF acts as the MAPK kinase kinase and activates MAPKK (MEK1/2), which in turn catalyze activation of the effectors ERK1/ERK2. Once activated, ERK1/2 translocate into the nucleus and phosphorylate a number of effector proteins and transcriptional factors that regulate cell proliferation, motility, differentiation, and survival. Trametinib is one of the several MEK inhibitors in clinical development.

Experience to date indicates that MEK is a valid target. In a phase III trial comparing trametinib with dacarbazine or paclitaxel in patients with BRAF V600E or V600K mutant metastatic melanoma, trametinib demonstrated a significantly better response rate, progression-free survival, and overall survival (Flaherty *et al.*, 2012). However, single agent activities are limited. Extensive research is underway to identify patient selection markers and develop rational combination strategies. Preclinical studies have provided strong rationale and proof of principle for combining MEK inhibitors with RTK inhibitors (EGFR or IGF-1R) (Gopal *et al.*, 2010; Ebi *et al.*, 2011), PI3K/AKT inhibitors (Engelman *et al.*, 2008; Hoeflich *et al.*, 2009), and mTOR inhibitors. On the other hand, the optimal dose/schedule and patient selection criteria for combination regimens have not been defined. Phase 1 results for a number of combinations have been reported, including AZD6244 + MK2206 (Tolcher *et al.*, 2011) and GDC-0973 + GDC-094 (MEK+ PI3K

inhibitor) (Bendell *et al.*, 2011).

5.6.1.3.1- Mechanisms of Action and Preclinical Data with Trametinib

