Patients with BRAFV600E positive Erdheim Chester disease will be enrolled in this study and will be evaluated at the NIH Clinical Center in Bethesda, Maryland. Patients will be referred to this trial from NHGRI protocol 11-HG-0207, which performs clinical and basic investigations into Erdheim Chester disease. Referrals will also be accepted from treating physicians, the ECD Global Alliance and patients themselves. Patient will be admitted for 4-5 days at the NIH Clinical Center and baseline testing will be performed prior to the first dose administration. Patients without progression or significant AEs may continue therapy for a maximum of 12 months. At six months, patients without RECIST- defined response or major clinical improvement may elect to discontinue therapy. There will be no randomization due to the rarity of the disease and small patient population. Patients will be seen once at the start of their participation in the trial, and again 1 week, 1 month, 2 months, 4 months, and 6 months, 8 months, 10 months and 12 months after the initial admission. At 12 months, therapy will be stopped and follow up will be for one year after completion of therapy at 15 months, 18 months and 24 months, but for proper analysis of treatment response and other variants, follow up could be prolonged. It is our intention to recruit at least 18 patients within approximately one year. In addition, we have access to approximately 100 cases in the USA and worldwide through the ECD Global Alliance. No placebo will be used and patients must stop their current ECD treatment at least 4 weeks before enrollment; this applies to cases in which the patient is not responding to current treatment.

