To determine the clinical response rate, baseline measurable disease, as per RECIST 1.1 criteria, will be determined less than 4 weeks prior to the start of treatment or at the baseline visit. Patients with ECD must have measurable or evaluable disease in one or more systems. These can include, but are not limited to, the retro-orbital space, pituitary stalk, cerebellum, brainstem, heart, retroperitoneal space causing renal and aortic encasement and long bones of upper and lower extremities. Complete response can be determined through imaging studies of these areas. As described in the treatment plan, imaging studies will be performed including retro-orbital/pituitary/brain/cerebellar MRI, abdomen and pelvis CT, and cardiac CT and MRI. FDG PET scan and T-99m bone scan will also be performed as exploratory outcome measures. The required imaging study will be selected on a case-by-case basis since the disease is heterogeneous in its presentation. Response to therapy will be evident on follow up imaging studies revealing a decrease in lesion size of 30% or more, which is defined as a partial response as per RECIST Criteria, when compared to baseline studies. After 12 months of therapy have been completed, patients will go to an off therapy follow up period that will have follow up visits at 15 months, 18 months and 24 months. During this period, duration of response will be assessed through

imaging studies of the patient's target lesions. If these target lesions show an increase, in at least one diameter, of 20% or more when compared to that target lesion measurement when they completed 12 months of therapy, this will be considered recurrence/progression of disease. Patients with disease recurrence will be considered for therapy resumption at the dose they were on when they completed therapy. Patients considered for therapy resumption will need to meet all inclusion and exclusion criteria and have new registration and TAC. They will also follow the safety guidelines for toxicity and dose modifications.

Besides imaging follow up, duration of response will be also assessed through patient's report of symptoms according to the MD Anderson symptom inventory, quality of life measures and SUV values on PET scan. Cytokines will also be followed during this period. All these parameters will help us determine disease recurrence-progression on each case.

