7.1.3- Analysis of Secondary Endpoints

As secondary evaluations, time to response, duration of response, PFS and OS will be reported separately using Kaplan-Meier curves and appropriate 95% confidence intervals. Every report will contain all patients included in the study. These findings will be compared informally to other similar published results in patients with the same disease.

Other exploratory analyses will include FDG-PET, CT, bone scans, and levels of C-reactive protein, ESR, and cytokines. There are no specific ECD biomarkers that can be measured in blood, urine or tissue in order to assess disease activity.

In patients affected by central nervous system disease (mainly cerebellar and brain stem disease), improvement in overall physical function and conditioning will be assessed. Patients will be evaluated by rehabilitation medicine and neurology. Improvement of their overall quality of life will be evidence of response, and assessments will be made at baseline and throughout the trial, as well as at the conclusion of the trial, to evaluate for any improvement in quality of life.

Resistance to therapy will be evaluated through imaging studies and patient follow up for at least one year, but this is not expected with the combination therapy.

7.1.4- Reporting and Exclusions

Evaluation of Toxicity

All patients will be evaluable for toxicity from the time of their first treatment with Dabrafenib mesylate (GSK2118436B, NSC 763760) and Trametinib dimethyl sulfoxide (GSK1120212B) (NSC 763093).

CTEP is the sponsor of the trial. The principal investigator and study data manager will monitor the safety data. CTEP will be notified of serious adverse events as soon as the PI, associate investigator or study data manager are aware of them through the expedited reporting systems and all AEs through the routine reporting to CDS. The National Human Genome Research Institute Intramural Data Safety and Monitoring Board (DSMB) will also monitor this trial. Monitoring by the DSMB will include receipt of quarterly updates regarding the trial status and accrual with a report every 6 months summarizing safety data as provided by the investigational staff. The DSMB will follow the protocols stopping

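### The off-therapy recurrence rule uses only the month-12 scan as reference, so it can miss or delay recurrence when a lesion was smallest before month 12, and it fails with no month-12 scan or a 0 mm lesion

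*Combined protocol and SAP*

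**What the plan says.** Section 7.1.1 sets out the off-therapy period: "After 12 months of therapy have been completed, patients will go to an off therapy follow up period", with visits at 15, 18 and 24 months. Duration of response is assessed in that period. The trigger is that target lesions "show an increase, in at least one diameter, of 20% or more", and the reference follows directly: "when compared to that target lesion measurement when they completed 12 months of therapy, this will be considered recurrence/progression of disease". Symptoms, quality of life, PET SUV and cytokines (Section 7.1.1) and PET and bone-scan uptake (Section 5.1.2) also inform the judgement of recurrence, without thresholds.

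For the treatment period, Section 5.1.2 says "These outcome measures will be assessed using RECIST criteria at every scheduled admission except the 1 week visit", and Table 4 schedules RECIST 1.1 measurements from week 8 to week 48. Response is defined against baseline, by scans "revealing a decrease in lesion size of 30% or more, which is defined as a partial response as per RECIST Criteria". Progression on therapy is a condition for continuing: "Patients without progression or significant AEs may continue therapy for a maximum of 12 months". No threshold or reference scan is printed for it. Section 7.1.4 lists progressive disease as a response category and leaves the precise definition to be protocol specific. Section 6.2.1 sends the reader to Section 11 for measurable disease, but Section 11 here is the risk/benefit assessment.

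Section 7.1.3 uses these events: "time to response, duration of response, PFS and OS will be reported separately using Kaplan-Meier curves". Every report is to contain all patients, and the results are compared informally with published ones.

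**The concern.** The fault lies in the reference scan. A patient whose lesions shrank to their smallest size at month 4 or 6 and were regrowing by month 12 starts the off-therapy year with the reference reset to the larger, month-12 size. Growth that began on therapy is then forgiven. Two other groups cannot be classified by the rule at all: patients with no month-12 scan, and patients whose target lesions measured 0 mm at month 12.

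Duration of response and PFS are at stake, and with them the reading of the resistance objective (Section 2.2.2), since the patients affected are those who begin to lose response during treatment. The comparison with published results also weakens if those results measured progression from a different reference.

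**Working it through.** The documents state no event count or power for duration of response or PFS, so there is no figure to reproduce. The inputs from the plan are the 20% threshold, the month-12 reference, the single-diameter unit and the visits at 15, 18 and 24 months (all Section 7.1.1). Growth rates, nadir timing and measurement error are assumptions.

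**1. Size of the forgiven growth.** Let N be the smallest measurement up to month 12, M the month-12 measurement and F a follow-up measurement. The plan calls an event when F/M >= 1.2; a smallest-value rule calls it when F/N >= 1.2. Since F/N = (F/M) x (M/N), a lesion with M/N just under 1.2 and F/M just under 1.2 reaches F/N just under 1.2 x 1.2 = 1.44. So growth of nearly 44% over the nadir can go uncounted even if on-therapy growth stayed below 20%. Because N <= M, the month-12 rule can never call the same lesion earlier than the smallest-value rule at the same threshold without measurement error.

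**2. A worked lesion.** It measures 30 mm at baseline and 15 mm at month 6 (-50%, a partial response).

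| Month | Size (mm) | Against month 12 | Against nadir |
|---|---|---|---|
| 12 | 17.5 | reference | +17% |
| 15 | 20.5 | +17% | +37% |
| 18 | 20.9 | +19% | +39% |

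The month-12 rule records no recurrence at either visit.

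**3. Records the rule cannot classify.** With M = 0 mm after a complete response and F = 12 mm, the change (12 - 0)/0 is undefined. With no month-12 scan there is no M.

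**4. Delay under steady regrowth.** Size = exp(rate x months since nadir). The rows below are cases not already past 20% on therapy.

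| Nadir (month) | Rate per month | Nadir rule calls at | Month-12 rule calls at |
|---|---|---|---|
| 4 | 1% | 24 | not by 24 |
| 4 | 2% | 15 | 24 |
| 6 | 2% | 18 | 24 |
| 6 | 3% | 15 | 24 |
| 8 | 3% | 15 | 24 |
| 8 | 4% | 15 | 18 |
| 10 | 2% | 24 | 24 |
| 10 | 3% | 18 | 24 |

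For example, with a nadir at month 4 and 2% per month, month 15 gives exp(0.22) = 1.25 over nadir but exp(0.06) = 1.06 over month 12. If month 12 is itself the nadir, the two rules agree at the first off-therapy visit.

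**5. How often.** Simulated lesions regrow exponentially from the nadir, with log-normal doubling times (median 12 to 48 months, log-SD 0.4) and no measurement error. Lesions that grew 20% over nadir on therapy are removed. Among recurrences that the nadir rule calls off therapy:

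| Nadir timing | Called late or missed by the month-12 rule | Missed altogether by month 24 |
|---|---|---|
| All at month 12 | 0% | 0% |
| 80% at month 12 | 5-23% | 0-12% |
| Even over months 4, 6, 8, 10, 12 | 36-71% | 0.1-37% |

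The higher figures belong to slower regrowth. In the last row, late or missed calls are 36%, 54%, 60%, 65% and 71% for median doubling times of 12, 18, 24, 36 and 48 months.

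**6. The opposite pull.** The trigger needs only one diameter. Lesions of 40 and 10 mm that become 40 and 12 mm count as recurrence (12/10 = +20%), although the sum moves from 50 to 52 mm (+4%). In simulated stable disease with three lesions, six on-therapy scans and a measurement CV of 5, 8 or 10%, false off-therapy recurrence is:

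| Rule | CV 5% | CV 8% | CV 10% |
|---|---|---|---|
| Any lesion against month 12 (the plan) | 4% | 32% | 50% |
| Any lesion against its smallest value | 22% | 86% | 97% |
| Sum of diameters against smallest sum | about 0% | 5% | 18% |

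Changing the reference while keeping the single-diameter trigger would therefore make matters worse.

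**The case against.** The strongest objection is that the rule covers only the off-therapy year. On-therapy scans are assigned to RECIST, so a responder who progresses at month 8 is judged under RECIST. This stands. A reader might infer that every relapse before month 12 goes unrecorded. Taking the melanoma median duration of response of 10.5 months for the 150/2 combination (Table 9) with exponential times, one could compute 1 - 2^(-(12-2)/10.5) = 48% of responses lost before month 12 when response starts at month 2. If those patients were censored, the 12-month proportion still in response would read 2^(-2/10.5) = 88% instead of 2^(-12/10.5) = 45%. The documents do not support that reading. Nothing says that on-therapy progressors are censored, and Section 7.1.4 counts progressive disease as failure in the response analysis. What remains is that on-therapy progression is cited but not written out, and is not reconciled with the month-12 rule.

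A second objection is that the progression definition may sit in text not supplied, since several cross-references do not match this document's numbering. That is possible. It would not cure the off-therapy rule, which is explicit and specific.

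Third, recurrence after a complete response could be called from PET, bone scan or symptoms. A reader might infer that it could never be recorded, and that goes too far. But those sources have no thresholds, so the event date is not reproducible.

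Fourth, the simulated frequencies depend on nadir timing, which the documents do not give, and Section 7.1.3 does not expect resistance. This stands, and it is why the range starts at 0%.

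Last, these are descriptive secondary curves in at most 18 patients. That limits the weight of the point without removing it.

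**Conclusion.** The point holds as a defect in a stated off-therapy rule. Followed exactly, the rule can leave growth of just under 44% over the nadir uncounted or call it late. It has no reference for a patient who stopped before month 12 and is undefined from 0 mm. Duration of response and PFS can be overstated in patients whose nadir came before month 12. How many are affected rests on assumed regrowth and nadir timing: 0% to 71% of nadir-based off-therapy recurrences called late or missed.

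A reader might go further and infer that both endpoints are overstated overall. The documents do not show that. The single-diameter trigger can shorten both, and the net direction depends on lesion number, regrowth and measurement error, none of which is given. The two-stage response decision uses the decrease from baseline and is unaffected. The point is worth correcting before analysis, but it does not threaten the trial's main conclusion.

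**What to change.** In Sections 7.1.1 and 7.1.3, state one RECIST 1.1-based progression definition for the analysis of duration of response and PFS, applied on and off therapy whether or not 12 months were completed. Suggested wording: *For duration of response and PFS, progression is an increase of 20% or more in the sum of target-lesion diameters over the smallest sum recorded on study (including baseline and month 12), at any visit on or off therapy. After a complete response, reappearance of a lesion is progression.*

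The reference and the unit must change together: a smallest-value reference should not be combined with the single-diameter trigger. The month-12 comparison can stay as a separate description of the off-therapy year. The clinical trigger for resuming therapy is for the sponsor to settle; the passages that use recurrence or progression should be reconciled.

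The cost is one or two sentences, using scans already scheduled. Reported durations may be shorter, and the analysis definition will differ from the off-therapy clinical trigger, which the text should say openly.

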The study will be conducted as an optimal Simon two-stage phase II trial in order to rule out an unacceptably low 10% clinical response rate (PR+CR: $p_0=0.10$) in favor of a targeted rate consistent with 40% ($p_1=0.40$). Maximum trial size would be set at 18 evaluable patients. If at least 4 responses (at least 22%) were observed among the 18 evaluable patients, this regimen would be considered worthy of further testing in this disease. If no responses were observed among the initial 6 patients, the study would be terminated early and declared negative. This design yields at least 90% power to detect a true response rate of at least 40%. It yields at least .90 probability of a negative result if the true response rate is no more than 10%, with at least .59 probability of early negative stopping. A temporary pause in the accrual to the trial may be necessary to ensure that enrollment to the second stage is warranted.

To ensure safety and feasibility of the selected dose for patients with ECD, we will assess the toxicity profile and dose delivery after the first 6 subjects have completed 3 months of therapy. If 3 or more individuals do not take at least 80% of the full doses of both drugs over 3 months due to dose modification for toxicity, revision of the dose schedule should be considered. Safety will be monitored on a continuous basis and feasibility of drug administration will be reviewed after 12 patients and then 18 patients have completed the 3 months of therapy.

All patients who receive any amount of the study drug will be evaluable for toxicity. Toxicity and doses adjustment will be perform as per the guidelines discussed on sessions 4.7 and 9 where dosing modifications and adverse events are discussed. Reassessment of the dose-schedule when 3 months or 12 cycles of therapy are completed will be performed by collecting the patient's medication diary information. This information will be collected by the study PI or the study coordinator by direct communication with the patient.

Besides response measured through imaging studies, physical and emotional well-being will be evaluated to assess improvement in daily living as exploratory endpoints. These

evaluations will be performed by the rehabilitation medicine and pain and palliative care teams during the treatment part of this trial as well as the off therapy follow up period. The list of tools and evaluations is available on sections 4.1.2 and 11.3.

7.1.2- Stratification Factors

N/A

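### The stated .59 chance of early stopping is wrong for a 6-patient first stage: the true value is .53, and both .59 and the label *optimal* fit a 5-patient first stage

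*Combined protocol and SAP*

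**What the plan says.** All the design inputs are in one paragraph of section 7.1.1 (Study Design/Endpoints).

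- Type of design: "The study will be conducted as an optimal Simon two-stage phase II trial".
- Hypotheses: the aim is to "rule out an unacceptably low 10% clinical response rate" (p0 = 0.10) against a target of 40% (p1 = 0.40).
- Size: "Maximum trial size would be set at 18 evaluable patients".
- Success rule: "If at least 4 responses (at least 22%) were observed among the 18 evaluable patients", the regimen merits further testing.
- Futility rule: "If no responses were observed among the initial 6 patients, the study would be terminated early and declared negative".
- Operating characteristics: power of at least 90% at a 40% response rate; at a rate of 10% or less, at least .90 probability of a negative result, "with at least .59 probability of early negative stopping".

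The text before review contains no 5-patient first stage. The same section also reviews toxicity and dose delivery after the first 6 patients have completed 3 months.

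**The concern.** The stopping rule and the stopping probability stand in the same paragraph and cannot both be right. The chance of no response in 6 patients at a given rate is a single power of one number and involves no modelling choice.

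Two things are at stake. First, early stopping under an ineffective regimen is what a two-stage design offers: it limits how many patients receive two drugs with substantial documented toxicity for no benefit. The stated figure makes that protection look stronger than it is. Second, the first-stage size becomes uncertain. The rule says 6, while the quoted probability and the optimality claim point to 5. A statistician or monitoring board member trying to reproduce the design cannot match both.

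**Working it through.** **Inputs**, all from section 7.1.1: p0 = 0.10, p1 = 0.40, first stage n1 = 6 with stop at r1 = 0 responses, maximum n = 18, success at 4 or more responses (r = 3). The error limits are read from the stated operating characteristics: type I error at most 1 − .90 = .10, and power at least .90.

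**Step 1. The stated figure.** Probability of early stopping = P(0 responses in n1) = (1 − p)^n1.

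- n1 = 6, p = 0.10: 0.9^6 = 0.5314.
- n1 = 5, p = 0.10: 0.9^5 = 0.5905.
- n1 = 4 gives .656 and n1 = 7 gives .478. Six patients with a stop at 1 or fewer responses gives .886.

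Only n1 = 5 with r1 = 0 reproduces .59 among these variants.

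**Step 2. Does the wording of a minimum help?** The claim covers all true rates up to 10%. Early stopping is least likely at the top of that range, so the guaranteed minimum is .531. To reach .59 with 6 patients needs (1 − p)^6 ≥ .59, that is p ≤ 1 − .59^(1/6) = 0.084. The claim is true only for rates of about 8.4% or lower.

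**Step 3. The other operating characteristics.** The probability of declaring success is the sum, over first-stage counts x from 1 to n1, of b(x; n1, p) × P(at least 4 − x responses in 18 − n1 patients). For the rule as written (n1 = 6, 12 patients in stage 2) at p = 0.10:

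| x in stage 1 | P(x) | P(success given x) | Product |
|---|---|---|---|
| 1 | .3543 | .1109 | .0393 |
| 2 | .0984 | .3410 | .0336 |
| 3 | .0146 | .7176 | .0105 |
| 4 or more | .0013 | 1 | .0013 |

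The products add to a type I error of .0846 (after rounding), so the probability of a negative result is .915. The same sum at p = 0.40 gives power of .931. Both meet the stated limits.

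Expected sample size at p0 = n1 + (18 − n1) × (1 − probability of early stopping):

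- n1 = 6: 6 + 12 × (1 − .5314) = 11.62.
- n1 = 5: 5 + 13 × (1 − .5905) = 10.32.

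**Step 4. Which design is optimal?** A Simon optimal design minimises expected sample size at p0 subject to the error limits. An exhaustive search over both stage sizes and both cut-offs, with type I error at most .10 and power at least .90, gives:

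| Design (stop if ≤ r1/n1, then negative if ≤ r/n) | Early stopping at 10% | Type I error | Power | Expected N at 10% |
|---|---|---|---|---|
| 0/5, 3/18 (optimal) | .590 | .078 | .903 | 10.32 |
| 0/6, 3/16 | .531 | .062 | .906 | 10.69 |
| 0/6, 3/18 (as written) | .531 | .085 | .931 | 11.62 |

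The optimal design shares with the plan the maximum of 18, the success rule of at least 4 responses and the .59. It differs only in the first-stage size. The rule as written is not the best even among 6-patient first stages, since 0/6 then 3/16 meets the same limits with a smaller expected sample size.

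**The case against.** The arithmetic on .59 has no good defence. Even if the figure is read as the chance of early stopping given a negative result, it is .531/.915 = .581, still short. The case on the other side concerns scope and weight.

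- **Optimality depends on the error limits, and the plan gives only floors.** If the required power is set at .925 or .93 with type I error at most .10, the minimum-expected-size design is exactly 0/6 then 3/18, the plan's own rule. This is correct. But the section states 90% and no higher requirement, and .59 fits only the 90% design. The statement that the design is not optimal is therefore conditional on limits of .10 and .10, which is the natural reading.
- **Little follows for the trial.** The stopping rule, success rule, maximum size, type I error and power claims are unaffected. The plan prints no expected sample size, so 10.3 is a comparison with the 5-patient design and not a second false statement; 41% is simply 1 − .59. This stands.
- **The rule is for futility, not toxicity.** Safety has its own reviews: after the first 6 patients, continuously, and by the monitoring board. This stands too. The effect on exposure is indirect, through how often an inactive regimen goes on to 12 more patients.
- **A first stage of 6 has a merit.** At a 40% rate the chance of wrongly stopping is 0.6^6 = .047, against 0.6^5 = .078 with 5 patients. This supports keeping 6; it does not support quoting .59.
- **The documents do not show which number was the slip.** This is true, and it is why the fix has to make the choice explicit.

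**Conclusion.** The concern holds. For the rule as written, the probability of early stopping at a 10% response rate is .531. The stated minimum of .59 is about 6 percentage points too high. The chance that a 10% regimen proceeds to the second stage is 46.9%, not the 41% or less that the stated figure implies. This part rests only on the binomial distribution and the plan's own numbers.

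The label *optimal* is also wrong under type I error of at most .10 and power of at least .90, limits inferred from the section's stated operating characteristics. Under them the optimal design has 5 patients in the first stage and an expected size of 10.32 at p0, against 11.62 for the rule as written. That the .59 was carried over from that 5-patient design is an inference, but it fits every figure.

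The claims on type I error (.085) and power (.931) are sound, and the final decision rule is valid. The error is in how the design is described, but it is a stated property that the design does not have, so it should be corrected.

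**What to change.** In section 7.1.1, keep the 6-patient first stage, which also coincides with the toxicity and dose-delivery review. Remove the word optimal. Replace the operating characteristics with: probability of early negative stopping .53 when the true rate is 10%; power .93 when it is 40%; type I error .085; expected sample size 11.6 when the true rate is 10%.

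The cost is wording only, with one figure becoming less favourable. No decision rule or sample size changes.

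The alternative is a 5-patient first stage. That would make .59 and *optimal* correct, with power .903 and type I error .078, but it changes the design, separates the futility look from the 6-patient review, and raises the chance of stopping a 40% regimen from .047 to .078.

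When the paragraph is edited, the Protocol Summary should be checked against it: its trial endpoint requires response in at least 3 of the first 6 patients. That is a different rule on the same six patients and is not the source of the .59.
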